7.2.2 Inclusion criteria

- 1. Written informed consent provided by the patient or legal representative for participating in the study (according to country specifications).
- 2. Age \geq 18 years.
- 3. Patients with symptomatic CHF (NYHA class II IV) with a documented reduced left ventricular ejection fraction (LVEF) as assessed by clinical examination and any imaging technique performed anytime in the past.

7.2.3 Exclusion criteria

- 1. Concomitant or planned participation in any interventional clinical trial
- 2. Patients who are receiving ongoing treatment with sacubitril/valsartan that has been started prior to market launch in their respective country, e.g. within a clinical trial or early access program.
- 3. Patient still within the safety follow up phase of any previous interventional or non-interventional trial using sacubitril/valsartan (LCZ696), independently whether they received sacubitril/valsartan or the comparator.
- 4. Acute decompensated HF requiring hospitalization at the moment of enrollment.
- 5. Existing contraindications according to approved product information

No additional restrictions for inclusion or exclusion are provided in order to ensure that the patients enrolled are as close as possible to (i.e. representative of) the real population of CHF patients with reduced LVEF managed in the office-based setting.

Page 21

7.3 **Variables**

- Demographics (age, gender, living at home or institution, relationship status, education)
- Medical history and comorbidity burden (with focus on duration of HF, etiology of CHF, last hospitalization for HF, cardiovascular conditions, specific comorbidities such as diabetes, renal insufficiency, COPD, anemia, obesity, cancer)
- Clinical Events (both retrospectively over the past 12 months and prospectively, as applicable):
 - Death (CV related and non-CV related, only prospectively)
 - Hospitalizations (defined as at least one overnight staying): number, elective or not, reason for hospitalization (CV related, HF related, non CV related)
 - **Myocardial Infarction**
 - Stroke
- Number of visits (other than hospitalization) by provider and primary reason during follow-up:
 - Emergency room/department
 - Outpatients office visits (general practitioner; cardiologist; internist; other specialist)
 - Cardiology (day) clinic
 - Device clinic
 - Nurse services/ day clinic
 - Rehabilitation facilities
- Diagnostic and therapeutic procedures utilized during follow-up (Results will be collected only as available for blood potassium, blood creatinine, BNP, NT-proBNP and for echocardiographic EF. In all other cases, the eCRF will only capture if the procedure has been performed and its primary reason)
 - Echocardiogram (LVEF in % if available)
 - ECG / stress ECG
 - Chest X ray
 - Pulmonary function tests
 - Computed Tomography of the Heart
 - Cardiac Magnetic Resonance Imaging
 - Cardiac catheterization
 - Coronary angiography
 - Percutaneous Coronary Intervention (PCI)
 - Coronary artery bypass graft surgery
 - Valve surgery
 - Aortic Valve Replacement (trans catheter or open heart)
 - Percutaneous mitral valve interventions
 - Devices implantation (pacemaker, ICD, CRT, CRT-ICD, LVAD)

- Heart transplantation
- 6-minute walk test
- Selected Laboratory tests (with no other specification)
- Blood potassium, blood creatinine, BNP and/or NT-proBNP levels (as per local lab)
- Referral pathway that brought the patient to the investigator (for patients who have been treated by the investigator for less than 6 months)
- Ongoing HF treatment and HF treatment received within the last 6 months prior to baseline, both pharmacological and non-pharmacological (physiotherapy, CRT, ICD, rehabilitation). As for ACE-I, ARBs, β-blockers, MRAs, diuretics and ivabradine: substance, dose and frequency of administration will be recorded. As for all other drugs, only the class will be recorded.
- Specifically for sacubitril/valsartan usage: dose at initiation, steps to up-titration, final dose. In case of lack of up-titration, of down-titration or discontinuation, the reason for it will be pursued and recorded in the eCRF.
- The proportion and baseline features of patients not reaching and maintaining the target dose of sacubitril/valsartan will be described: consistently with the definition adopted in the TITRATION study, the target dose is defined as "achieving and maintaining sacubitril/valsartan 200 mg bid without any down-titration or dose interruption over 12 weeks".
- Vital signs (blood pressure, pulse, NYHA status, HF signs and symptoms)
- EQ-5D and/or Kansas City Cardiomyopathy Questionnaire (KCCQ) only in those sites where these questionnaires are part of the routine management of CHF and thus their completion does not affect the non-interventional nature of the present NIS.
 - The EQ-5D (Dolan 1997) is a widely used generic questionnaire designed to assess health status in adults. The measure is divided into two distinct sections. The first section includes one item addressing each of five dimensions (mobility, self-care, usual activity, pain/discomfort, and anxiety/depression). The second section of the questionnaire measures self-rated (global) health status utilizing a vertically oriented visual analogue scale where 100 represents the "best possible health state" and 0 represents the "worst possible health state". This questionnaire will be completed by the patient and collected by the investigator, who will immediately check the questionnaire for remarks by the patient that could indicate adverse events; thereafter the EQ-5D will be entered into the eCRF by the site staff.
 - The KCCQ is a HF-specific questionnaire (Allen, Gheorghiade et al. 2011) and requires on average 4-6 minutes to complete. It covers physical function, clinical symptoms, social function, self-efficacy and knowledge, and Quality of Life (QoL), each with different Likert scaling wording, including limitations, frequency, bother, change in condition, understanding, levels of enjoyment and satisfaction. The KCCQ is a valid, reliable and responsive health status measure for patients with heart failure. This questionnaire will be completed by the patient and collected by the investigator, who will immediately check the questionnaire for remarks by the patient that could indicate adverse events; thereafter the EQ-5D will be entered into the eCRF by the site staff.

 Adverse Events (AEs)/ Adverse Drug Reactions(ADRs) and Serious AEs (SAEs)/Serious ADRs (see Section 9).

7.4 Data sources

This is an observational study with prospective data collection. For some variables, retrospective data shall also be obtained from the patients' medical records (e.g. healthcare utilization in the past 12 months, medical history, prior CHF therapy). The study comprises three visits: at baseline and at approximately 6 months and 12 months after baseline. No exact dates will be enforced for patient visits to avoid interference with usual care. Patients will be enrolled on a consecutive basis. Patient records at the site will be regarded as source data. Sites will be monitored as described in the monitoring plan.

Physicians will record data in an electronic case report form (eCRF) provided by Novartis or designated CRO, which will capture, check, and store the data. The treating physician is asked to complete the eCRF at the time of each visit.

Where applicable, i.e. in countries where these are part of the routine management of CHF, the KCCQ and EQ-5D QoL questionnaires will be applied. The KCCQ and the EQ-5D QoL questionnaire will be completed by the patient, thereafter immediately (within 24 hours) checked by the investigator for remarks hinting at an otherwise unreported adverse event, and subsequently entered by the site staff into the eCRF.

The administration of both questionnaires will occur at baseline (after signature of the ICF and enrollment into the NIS), and during the following 2 visits (around 6 and 12 months after).

Safety data will be transferred to Novartis at a frequency as defined in section 8 of this protocol. Clinical data will be transferred to Novartis after closure of the study.

Data collection schedule

This is a non-interventional study. Therefore no visit schedule will be imposed on participants to avoid interference with routine clinical care. However, based on clinical experience, it seems reasonable to assume that patients visit their treating physicians at least twice a year. Data will be recorded at visits closest to 6 and 12 months (recommended visit window \pm 2 months), performed according to the investigator's practice and judgement. Patients will be treated according to the local prescribing information, and routine medical practice in terms of visit frequency and types of assessments performed and only these data will be collected as part of the study. All items recorded derive from routine clinical care, except informed consent, QoL questionnaires (KCCQ and EQ-5D) and measurements of NT-proBNP blood levels. Therefore, NT-proBNP assessments and QoL questionnaires will be obtained only as available and in those sites where they are part of routine CHF management and thus will not compromise the non-interventional nature of the trial. In all other sites, NT-proBNP testing will be recorded only if available due to the investigator's decision and his/her routine practice and QoL questionnaires will not be assessed.

In general, if any assessment is not done, or information is not available from routine clinical care, this will be documented accordingly.

	Baseline	6 months*	12 months*
Informed consent	Х		
Demographics	X	X ⁺	X ⁺
Etiology of HF	X		
History of HF and CV events	X		
Comorbidities	X	X	X
Referral pathway (as applicable)	X		
Vital signs, HF signs and symptoms	X	X	X
Diagnostics and therapeutic procedures	X	X	X
NT-proBNP (as available)	X	X	X
CHF treatment	\mathbf{X}^{1}	X	X
LCZ696 dose and titration§	X	X	X
QoL questionnaires#	X	X	X
Adverse Events/ADR/SAE/SADR	X	X	X
Healthcare resource utilization		X	X
End of study assessment			X

^{*}The recommended visit window should be within 2 months before or after the planned date

ADR – Adverse Drug Reactions, SAE – Serious Adverse Event, SADR – Serious ADR LCZ696 = sacubitril/valsartan

Patients may withdraw consent to continue participation in the registry for any reason at any time. If a patient withdraws consent, the investigator must make every effort to determine the primary reason for this decision and record this information.

For patients who are missing their appointment of the Follow-up visits, without having stated an intention to withdraw consent, the investigator is asked to exercise "due diligence" by contacting the patient or family or other treating physician, as agreed in the informed consent. These efforts should be documented and any information relevant to the missed visit completed in the eCRF.

[#] Only in sites, where part of routine medical management of CHF

[§] Only for patients who receive sacubitril/valsartan

⁺ only if relevant changes to certain aspects occurred between visits

¹ only CHF treatment required that is either ongoing at baseline or has been changed within the last 6 month prior to baseline

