Note: The decision to treat a patient with individualized currently available therapies (SoC) or to start sacubitril/valsartan is to be taken by each investigator according to his/her clinical judgment and independently form participation in this study. Only after that decision is taken, the patient will be enrolled, in order to respect and describe real world clinical practice.

Every effort will be made to reduce selection bias by enrolling patients on a consecutive basis. This also means that patients, who already have been initiated on sacubitril/valsartan treatment after the drug has become commercially available can be included into the study, if they satisfy all inclusion and exclusion criteria and the investigator has the sufficient baseline information (see Section 7.3) on file for these patients.

Follow-up for all patients will last up to 12 months after the baseline visit. The follow-up will consist of 2 visits closest to 6 months and 12 months after the baseline visit, respectively (recommended visit window of \pm 2 months). No exact date for the second and final visits will be enforced, to avoid interference with the real life routine care. In case intermediate visit (6 month) will not take place, this will be recorded and described as part of real world practice.

At any time during the study, the investigator is free to adapt or change the patient's CHF treatment as per his/her clinical judgement at any time – the reasons for switching treatments as well as specific details of the new CHF treatment will be documented. The duration of the patient's follow-up is not altered by the switching of therapy, i.e. the individual follow-up duration is only dependent on the time point of the enrollment.

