7.7 Data analysis

All analyses will be performed by the designated CRO.

Only descriptive data analyses will be carried out, supported by calculation of confidence intervals. No statistical testing will be performed.

The two patient populations will be considered and analyzed separately. The SoC group will allow the representative picture of current CHF management as mentioned above. The Sacubitril/valsartan stratum will provide early insight into the adoption of this new therapy, once it will be available in the different countries. Therefore also strata for patients switching between SoC and Sacubitril valsartan will be analyzed upon adequate subgrouping.

The two studied groups, SoC and sacubitril/valsartan, are expected to differ significantly depending on the progressive adoption of sacubitril/valsartan by the prescribers – this will be assessed by stratified analysis according to the above described enrollment phases. In addition, besides baseline characteristics of the patients leading to the physicians' decision to prescribe sacubitril/valsartan or continue SoC, no inferences can be made from the comparison of the characteristics of both populations. For the same reason, no comparison of data obtained during the follow-up phase between the treatment groups is planned. Similarly, no safety comparisons will be performed between SoC (where in most cases an established therapy is merely continued) and sacubitril/valsartan (where a new therapy is prescribed).

Analyses will be performed for the total sample and stratified by demographic, anamnestic and medical factors (e.g. sex, duration of HF, severity of HF, previous HF-treatment) using an adequate grouping. Similarly, data will be also analyzed stratified according to enrollment phase (phase 1 and phase 3) and treatment group (e.g. SoC, valsartan/sacubitril, switching between both groups).

The Statistical Analysis Plan will be created as a separate document prior to data base lock for any analysis (e.g. interim analyses, final analysis). This document will contain sufficient details to enable the generation of the analysis of the NIS and specifies:

- the statistical database underlying the evaluation, including all adjustments, implementations and the calculation of derived variables,
- the detailed establishment of the analyzed population(s), and
- the statistical procedures.

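### Patients already on sacubitril/valsartan may enter at any time since first dose, but heart failure therapy is required only for the 6 months before baseline, so the therapy it replaced may be missing

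*Protocol*

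**What the plan says.** **Who may enter.** Section 7.2.1 allows that "patients, who already have been initiated on sacubitril/valsartan treatment after the drug has become commercially available can be included into the study", provided "the investigator has the sufficient baseline information (see Section 7.3) on file for these patients". The only bound on when the drug was started is in Section 7.2.3, which excludes "ongoing treatment with sacubitril/valsartan that has been started prior to market launch in their respective country". No maximum time since first dose is set. Figure 7-1 gives 24 months for overall enrollment.

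**What treatment history is required.** Section 7.3 lists "Ongoing HF treatment and HF treatment received within the last 6 months prior to baseline, both pharmacological and non-pharmacological". Substance, dose and frequency are recorded for the main drug classes, and class only for the rest. Footnote 1 to the data collection table in Section 7.4 narrows the baseline entry for CHF treatment: "only CHF treatment required that is either ongoing at baseline or has been changed within the last 6 month prior to baseline". The Section 7.4 text gives "medical history, prior CHF therapy" among its examples of retrospective data, but states no window for prior therapy.

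**Which date is baseline.** Informed consent is taken at the baseline visit (data collection table), Section 9 equates that visit with the start of study, and Section 7.2.1 says that "the individual follow-up duration is only dependent on the time point of the enrollment". Nothing resets baseline to the first dose for patients already treated.

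**How the history is used.** Section 7.7 plans analyses "stratified by demographic, anamnestic and medical factors (e.g. sex, duration of HF, severity of HF, previous HF-treatment". An additional objective in Section 6 describes starting dose, titration and maintenance dose by anamnestic and demographic characteristics.

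**The concern.** The entry rule is open-ended backwards to launch, while the treatment look-back is fixed at 6 months before enrollment. The protocol's abstract describes sacubitril/valsartan as designed to take over the role of an ACE inhibitor or ARB, so the replaced drug is normally no longer ongoing once the switch is made. If the switch lies more than 6 months back, the replaced drug falls outside both parts of the rule.

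One label then carries two meanings. For a new starter, previous HF treatment is what the patient took before sacubitril/valsartan. For a long-treated entrant it is blank, or it describes therapy after the switch. Whether the history is present depends on time since initiation. Entrants still on the drug after more than 6 months have had longer to titrate and have stayed on it, so the gap is unlikely to be unrelated to titration results. An SAP can define the stratum, but it cannot restore data that were never collected.

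**Working it through.** The plan gives no figure on this point to reproduce. The check sets the rules side by side and then illustrates the possible size.

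**1. The rules applied to one patient at two enrollment dates**

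| | Enrolled on the day of the switch | Enrolled 9 months after the switch |
|---|---|---|
| Admitted under Sections 7.2.1 and 7.2.3 | Yes | Yes, if the start was after launch |
| Replaced drug ongoing at baseline | No, stopped that day | No |
| Replaced drug received or changed within 6 months before baseline | Yes | No |
| Record of that drug and dose required | Yes | No |

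Section 7.3 says received within 6 months and footnote 1 says changed within 6 months. Both leave out the drug in the right-hand column.

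**2. Does other text close the gap?**
- The entry condition on baseline information points to Section 7.3, which has the same 6-month limit.
- The mention of prior therapy in Section 7.4 sets no longer window, and footnote 1 in the same section is restrictive.
- Section 7.3 asks for the sacubitril/valsartan dose at initiation and the titration steps, with no time limit. The plan thus reaches back to initiation for the new drug but not for the therapy that it replaced.

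**3. Illustrative size**

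Assumptions, none of them from the protocol: already-treated patients enter at a time t uniform on (0, T) months since launch, and their first dose is uniform on (0, t).

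For t > 6, the chance of a start more than 6 months before entry is (t − 6)/t. Averaged over t:

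share = [(T − 6) − 6 ln(T/6)] / T

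- T = 6: 0%
- T = 12: (6 − 6 × 0.693)/12 = 0.153, about 15%
- T = 18: (12 − 6 × 1.099)/18 = 0.300, about 30%
- T = 24: (18 − 6 × 1.386)/24 = 0.403, about 40%

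These are shares of already-treated entrants, not of the whole group. How many of the 6000 sacubitril/valsartan patients enter already treated is not stated. Over an assumed range of 10% to 50%:

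- T = 12: 6000 × 0.10 × 0.153 ≈ 92, to 6000 × 0.50 × 0.153 ≈ 460
- T = 24: 6000 × 0.10 × 0.403 ≈ 242, to 6000 × 0.50 × 0.403 ≈ 1210

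Across these assumptions, that is about 1.5% to 20% of the group.

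**The case against.** A bounded look-back is an ordinary trade-off in a chart-based non-interventional study, and Section 7.9 already lists the absence of stipulations on prior treatments as a limitation. The affected subset may also be small. Enrollment begins in each country when the drug becomes available, sacubitril/valsartan enrollment is continuous, patients are to be taken consecutively, uptake is expected to be slow at first, and patients are assumed to be seen at least twice a year. At a site active from launch, most already-treated patients would be met within about 6 months of starting. This stands as a reason to expect numbers towards or below the low end. It is not a safeguard: no rule limits time since first dose, a site that opens late would meet longer-treated patients, and Section 7.9 concedes that consecutive enrollment cannot be verified.

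A reader might infer more than the documents support:

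- *That only the sacubitril/valsartan group is affected.* The 6-month rule applies to everyone. An SoC patient whose ACE inhibitor was stopped 9 months earlier loses that record too. What is particular to the sacubitril/valsartan group is the loss of the therapy that the study drug replaced.
- *That the main objectives are biased.* The profiles in Sections 6 and 7.5 list demographics, medical history, HF status and comorbidity burden. Prior drug therapy is a separate variable in Section 7.3 and enters as an example stratifier.
- *That patients will be misclassified as never having had an ACE inhibitor or ARB.* Not required is not the same as recorded as none, sites may enter more, and Section 7.4 says unavailable information is documented as such. The defect is missing data, and it becomes misclassification only if a blank is read as none.
- *That half to three quarters of already-treated entrants fall outside the window.* Time since first dose uniform over 12 or 24 months gives 1 − 6/12 = 50% or 1 − 6/24 = 75%, but this treats every such patient as enrolled at the very end of the period.
- *That the missing share can be set against the ±1.3% precision in Section 7.5.* That figure is a sampling half-width. A share of missing records is not a bias of the same size.

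**Conclusion.** The mismatch between entry rule and look-back is real and follows from the text alone. For entrants who switched more than 6 months before the baseline visit, nothing requires the replaced therapy or its dose to be recorded. The consequence is limited to analyses that use previous HF treatment: the stratification in Section 7.7 and, where treatment history counts as an anamnestic characteristic, the Section 6 description of dosing and titration. The listed main-objective profile variables are untouched, and background therapy still ongoing at baseline is captured.

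The size cannot be derived from the protocol. About 15% to 40% of already-treated entrants is an illustration that rests on uniform entry and start times and on 12 to 24 months since launch. The patient counts also need an assumed share of already-treated entrants. Both would fall if consecutive enrollment from launch is kept. The change is worth making because it is cheap and data not collected at entry may be hard to recover later.

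**What to change.** In Section 7.3 and footnote 1 of the data collection table, add a rule for patients already taking sacubitril/valsartan at enrollment. Require the date of first dose, and the heart failure treatment (substance, dose and frequency, at the detail Section 7.3 already sets) that was ongoing at that date or changed in the 6 months before it, as available in site records. Keep the present window before the baseline visit for all other patients.

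Derive previous HF treatment from the pre-first-dose window for the already-treated entrants, and code unavailable data as unknown, not as none.

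The cost is one sentence, one amended footnote, a few eCRF fields, and a small amount of extra chart review for already-treated entrants only. The change concerns data collection and does not touch treatment.
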